4.3 Selection of Study Population

This will be a single site study conducted at the Mirpur field site by the icddr,b. The first part (Part A) will enroll a total of 45 adult participants (30 vaccinees and 15 placebos) into one Cohort. The second part (Part B) will enroll a total of 150 toddlers (24-29 months) into 6 separate cohorts to be recruited in step-wise

fashion. Each cohort will enroll 25 toddlers (15 vaccinees and 10 placebos). The third part (Part C) will enroll a total of 100 younger children (12-23 months) into 4 separate cohorts in a step-wise fashion. Each cohort will enroll 25 younger children (15 vaccinees and 10 placebos). The fourth part (Part D) will enroll a total of 200 infants (6-11 months) into 5 separate cohorts to be recruited in a step-wise fashion. Each cohort will enroll 40 infants (30 vaccinees and 10 placebos). Toddlers, younger children and infants will only be enrolled if their parents are fully informed about the study and provide consent for their child's participation.

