9.1.2 Unsolicited Adverse Events

The proportion of participants reporting at least one unsolicited adverse event will be summarized by MedDRA system organ class and preferred term for each treatment group and overall. Denominators for percentages are the number of participants in the Safety population. A 95% CI calculated using Clopper-Pearson methodology from a binomial distribution (SAS Proc Freq with a binomial option) will be presented for each MedDRA system organ class and preferred term (Tables 14.3.1.7(a)(b)(c)(d))

Unsolicited adverse events by participant will be presented in Listings 16.2.7.2(a)(b)(c)(d).

The following summaries for unsolicited adverse events will be presented by treatment group:

- Participant level summary of maximum severity and relationship to study product by MedDRA SOC and PT (Tables 14.3.1.8.1(a)(b)(c)(d));
- Participant level summary of related unsolicited events by maximum severity, MedDRA SOC and PT (Tables 14.3.1.8.2(a)(b)(c)(d));
- Participant incidence of unsolicited adverse events over time by MedDRA SOC and PT (Days 1-8, Days > 8) (Tables 14.3.1.9.1(a)(b)(c)(d));
- Participant incidence of related unsolicited adverse events over time by MedDRA SOC and PT (Days 1-8, Days > 8) (Tables 14.3.1.9.2(a)(b)(c)(d));
- Total frequency of adverse events over time by MedDRA SOC and PT (Days 1-8, Days > 8) (Tables 14.3.1.10(a)(b)(c)(d));
- Participant listing of non-serious adverse events of moderate or greater severity (Tables 14.3.2.2(a)(b)(c)(d));
- Bar chart of the frequency of events for non-serious adverse events by maximum severity and MedDRA SOC (Figures 14.3.1.11(a)(b)(c)(d));
- Bar chart of the percent of participants reporting a non-serious adverse event by maximum severity and MedDRA SOC (Figures 14.3.1.12(a)(b)(c)(d));
- Bar chart of the frequency of any adverse event by maximum severity (Figures 14.3.1.13(a)(b)(c)(d));
- Bar chart of the percent of participants of any adverse event by maximum severity (Figures 14.3.1.14(a)(b)(c)(d));
- Bar chart of the frequency of non-serious adverse events by relationship to treatment and MedDRA SOC (Figures 14.3.1.15(a)(b)(c)(d));

- Bar chart of the percent of participants of non-serious adverse events by relationship to treatment and MedDRA SOC (Figures 14.3.1.16(a)(b)(c)(d));
- Bar chart of the frequency of any adverse event by relationship to treatment (Figures 14.3.1.17(a)(b)(c)(d)).

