FIGURE 14.3.1.12a: Incidence of Non-Serious Adverse Events by MedDRA® System Organ Class and Maximum Severity - Adults

Programming Note: Continue for all MedDRA System Organ Classes.

FIGURE 14.3.1.12b:

Incidence of Non-Serious Adverse Events by MedDRA® System Organ Class and Maximum Severity - Toddlers (24 - 59 Months)

Programming Note: Use same format as Figure 14.3.1.12a - except use treatment groups: ETVAX 3.5 mL, ETVAX 7mL, ETVAX 14 mL, ETVAX ## + 2.5 μ g dmLT, ETVAX ## + 5 μ g dmLT, ETVAX ## + 10 μ g dmLT, Placebo

FIGURE 14.3.1.12c:

Incidence of Non-Serious Adverse Events by MedDRA® System Organ Class and Maximum Severity - Young Children (12 - 23 Months)

[figure not shown]
Programming Note: Use same format as Figure 14.3.1.12c - except use treatment groups: $ETVAX\ 3.5\ mL$, $ETVAX\ 7mL$, $ETVAX\ ## + 2.5\ \mu g\ dmLT$, $ETVAX\ ## + 5\ \mu g\ dmLT$, Placebo

FIGURE 14.3.1.12d:

Incidence of Non-Serious Adverse Events by MedDRA® System Organ Class and Maximum Severity - Infants (6 - 11 Months)

Programming Note: Use same format as Figure 14.3.1.12d - except use treatment groups: ETVAX 1.75 mL, ETVAX 3.5 mL, ETVAX 7mL, ETVAX ## + 2.5 µg dmLT, ETVAX ## + 5 µg dmLT, Placebo

FIGURE 14.3.1.13a: Frequency of Adverse Events by Severity - Adults

Note: This Figure includes serious and non-serious adverse events.

FIGURE 14.3.1.13b: Frequency of Adverse Events by Severity - Toddlers (24 - 59 Months)

Programming Note: Use same format as Figure 14.3.1.13a - except use treatment groups: ETVAX 3.5 mL, ETVAX 7mL, ETVAX 14 mL, ETVAX ## + 2.5 μ g dmLT, ETVAX ## + 5 μ g dmLT, ETVAX ## + 10 μ g dmLT, Placebo

[figure not shown]
FIGURE 14.3.1.13c: Frequency of Adverse Events by Severity - Young Children (12 - 23 Months)

Programming Note: Use same format as Figure 14.3.1.13a - except use treatment groups: ETVAX 3.5 mL, ETVAX 7mL, ETVAX ## + 2.5 μ g dmLT, ETVAX ## + 5 μ g dmLT, Placebo

FIGURE 14.3.1.13d: Frequency of Adverse Events by Severity - Infants (6 - 11 Months)

Programming Note: Use same format as Figure 14.3.1.13a - except use treatment groups: ETVAX 1.75 mL, ETVAX 3.5 mL, ETVAX 7mL, ETVAX ## + 2.5 µg dmLT, ETVAX ## + 5 µg dmLT, Placebo

FIGURE 14.3.1.14a: Incidence of Adverse Events by Maximum Severity - Adults

Note: This figure includes both serious and non-serious unsolicited adverse events. The maximum severity for a participant will be summarized.

FIGURE 14.3.1.14b: Incidence of Adverse Events by Severity - Toddlers (24 - 59 Months)

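### In Parts B to D the adverse event frequency charts and Table 14.3.1.10b-d show event counts undivided by arm size, so at planned sizes equal event rates would give pooled placebo 1.7 to 4.0 times the events of each single dose arm

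*SAP*

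**What the plan says.** SAP section 9.1.2 plans two families of bar chart for unsolicited adverse events. One family shows frequency: Figures 14.3.1.11, .13, .15 and .17, the first described as "Bar chart of the frequency of events for non-serious adverse events by maximum severity and MedDRA SOC". The other shows the percentage of participants: Figures 14.3.1.12, .14, .16 and .18. The titles in the appendix keep the distinction, with frequency in one family and incidence in the other; an example of the first is "FIGURE 14.3.1.13b: Frequency of Adverse Events by Severity - Toddlers (24 - 59 Months". Table 14.3.1.10 tabulates numbers of events by system organ class, preferred term and time window, with no rate column.

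The programming notes for the Part B, C and D figures list each dose arm separately and a single placebo group. Table 14.3.1.10b-d has the same single arms and placebo, and adds combined columns: ETVAX alone, ETVAX with dmLT, and all vaccine.

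Section 4.3 fixes the planned sizes. Toddlers: "a total of 150 toddlers (24-29 months) into 6 separate cohorts" and "Each cohort will enroll 25 toddlers (15 vaccinees and 10 placebos". (The 24-29 month range there differs from the 24-59 months used elsewhere; it does not affect the counts.) Young children: "a total of 100 younger children (12-23 months) into 4 separate cohorts" and "Each cohort will enroll 25 younger children (15 vaccinees and 10 placebos". Infants: "a total of 200 infants (6-11 months) into 5 separate cohorts" and "Each cohort will enroll 40 infants (30 vaccinees and 10 placebos".

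**The concern.** A count of events depends on both the event rate and the number of people who could have events. Where arms are of similar size the count is a fair summary. In Parts B to D they are not: the placebo group collects the controls from four to six cohorts, while each dose arm draws on one. Differences in bar height then largely reflect arm size.

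This matters because adverse events are among the primary endpoints (section 3.2.1), and the frequency charts are the displays meant to show how many events occurred. Section 9.1 counts each participant once for incidence and ignores repeats, so the percentage charts answer a different question. A reader who compares bars across arms could be misled about relative event burden.

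**Working it through.** **Reproducing the plan's totals** (section 4.3), as cohorts × (vaccinees + placebos):
- Part B: 6 × (15 + 10) = 150, as stated.
- Part C: 4 × (15 + 10) = 100, as stated.
- Part D: 5 × (30 + 10) = 200, as stated.

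**Pooled placebo per Part**, as cohorts × 10: Part B 60, Part C 40, Part D 50. Each single dose arm has 15, 15 and 30 respectively.

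**Ratio of counts under equal rates.** If every arm has the same mean number of events per participant, r, the expected counts are N(placebo) × r and N(arm) × r. The ratio is N(placebo) / N(arm), whatever r is.

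| Part | Placebo N | Single dose arm N | Ratio |
|---|---|---|---|
| B, toddlers | 60 | 15 | 60/15 = 4.0 |
| C, young children | 40 | 15 | 40/15 = 2.67 |
| D, infants | 50 | 30 | 50/30 = 1.67 |

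**Combined columns of Table 14.3.1.10.** From the arms listed in section 4.4.2, planned combined sizes are: Part B 3 × 15 = 45 alone, 3 × 15 = 45 with dmLT, 90 in all; Part C 2 × 15 = 30, 2 × 15 = 30 and 60; Part D 3 × 30 = 90, 2 × 30 = 60 and 150.

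| Part | Placebo / alone | Placebo / with dmLT | Placebo / all vaccine |
|---|---|---|---|
| B | 60/45 = 1.33 | 60/45 = 1.33 | 60/90 = 0.67 |
| C | 40/30 = 1.33 | 40/30 = 1.33 | 40/60 = 0.67 |
| D | 50/90 = 0.56 | 50/60 = 0.83 | 50/150 = 0.33 |

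The same table thus inflates placebo relative to single arms and deflates it relative to the all-vaccine column.

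**Illustration, with assumed rates that the SAP does not give.** With 3 events per participant in one toddler dose arm and 1 per participant on placebo, the counts are 15 × 3 = 45 and 60 × 1 = 60: the arm with three times the rate has the shorter bar.

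**After dividing by N**, equal rates give a ratio of 1.0 in every comparison.

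**Adults.** Allocation in Part A is 1:1:1, so the ratio is 1.0 and the problem does not arise.

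**The case against.** The strongest reply is that the reader already has what is needed. Each frequency chart has a percentage chart for the same breakdown. Tables 14.3.1.7 to 14.3.1.9 give percentages, the first with exact confidence intervals. Table 14.3.1.10 carries N in its column headings, so a reader can divide. The primary endpoints are proportions, and no test rests on the count displays. All of this stands, and it keeps the point minor. It does not remove it: the percentages set repeat events aside, and no output listed in the SAP gives events per participant.

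A second reply is that the figure images are not shown. The count axis is an inference from section 9.1.2 and the titles, and N may be printed on the panels, as it is in the surviving label of Figure 14.3.1.4a. That is fair. Even with N printed, bar heights on a count scale would still follow arm size.

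A third concerns Table 14.3.1.10. The notes under Tables 14.3.1.10b and c say a participant is counted once per term and class within a period, which contradicts a count of events. Whether that table captures repeats is therefore unsettled. Either way, the count is not divided by N.

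Two stronger readings are tempting. A reader might infer that these displays favour the vaccine throughout. At planned sizes that holds for the single arms, but the combined columns show it does not hold generally. A reader might also set the 5 full-dose recipients in the footnote to Tables 14.3.1.6.1 and 14.3.1.6.2 against 60 placebo toddlers and get 12-fold. That mixes an actual count with a planned one, and the SAP does not give the other actual arm sizes.

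**Conclusion.** The point holds for Parts B to D. With equal event rates and planned arm sizes, the undivided counts would show placebo with 4.0 (toddlers), 2.7 (young children) and 1.7 (infants) times the events of each single dose arm. In the combined columns of Table 14.3.1.10 the ratio is 1.33 or lower; it falls below 1 for all vaccine combined in every Part and for every combined column in infants. The direction of the distortion depends on the column.

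This rests on three assumptions: arms fill as planned, placebo is pooled within each Part as the shells indicate, and the frequency figures use a count axis. Adults are unaffected. Severity is low, because no inference depends on these displays and a careful reader can partly correct for arm size.

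**What to change.** For Parts B to D:
- Plot events per participant, or per 100 participants, in Figures 14.3.1.11, .13, .15 and .17, with N shown for each arm.
- Add the same rate beside the number of events in Table 14.3.1.10b-d.
- Correct the note under Tables 14.3.1.10b and c so that it agrees with a count of events, and state whether repeat events in one participant are counted.

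The cost is one division in existing programs and an edited footnote; no data collection or test changes. The one drawback is that rates in very small arms are unstable, since one child with several events can move the figure a long way. Keeping the counts next to the rates deals with that.

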				# of Days				
	Treatment			Post Dose	Duration		Relationship to	Action Taken with
Participant ID	Group	Onset Date	Adverse Event	(Dose #)	(Days)	Severity	Study Treatment	Study Treatment

Participant ID	Adverse Event	Outcome	Comments

TABLE 14.3.2.2b:

Listing of Non-Serious, Unsolicited, Moderate or Severe Adverse Events - Toddlers (24 - 59 Months)

Programming Note: Use the same Table shell as Table 14.3.2.2(a).

TABLE 14.3.2.2c:

Listing of Non-Serious, Unsolicited, Moderate or Severe Adverse Events - Young Children (12 - 23 Months)

Programming Note: Use the same Table shell as Table 14.3.2.2(a).

TABLE 14.3.2.2d:

Listing of Non-Serious, Unsolicited, Moderate or Severe Adverse Events - Infants (6 - 11 Months)

Programming Note: Use the same Table shell as Table 14.3.2.2(a).

Section 14.3.3: Narratives of Deaths, Other Serious and Significant Adverse Events

[This is a place holder for this section in the CSR]

TABLE 14.3.4.1a: Laboratory Results by Parameter, Maximum Severity, Study Day, and Treatment Group - Adults

							A	ny La	borate	ory Par	amete	r										
						Mild/ (Grade	1	Mo	derate/	' Grad	le 2	S	Severe/C	Grade	3	L		reater	ning/		
			N	one	(L	ow)	(H	igh)	(I	ow)	(Hi	igh)	(L	ow)	(H	igh)	(L	ow)	(H	igh)	Mis	sing
Time Point	Treatment Group	N	n	%	n	%	n	%	n	%	n	%	n	%	n	%	n	%	n	%	n	%
Baseline	Placebo	X	X	x.x	X	X.X	X	X.X	X	X.X	X	x.x	X	X.X	X	X.X	X	x.x	X	X.X	X	X.X
	ETVAX Full Dose	X	X	x.x	X	X.X	X	x.x	X	X.X	X	x.x	X	X.X	X	X.X	X	x.x	X	X.X	X	x.x
	ETVAX Full Dose + 10 μg dmLT	X	х	X.X	х	x.x	Х	X.X	Х	x.x	Х	X.X	Х	x.x	Х	X.X	X	X.X	X	x.x	Х	X.X
Day 7	Placebo	X	Х	x.x	X	X.X	х	X.X	х	X.X	х	x.x	X	X.X	х	X.X	X	x.x	X	x.x	X	X.X
	ETVAX Full Dose	X	Х	x.x	X	X.X	Х	X.X	Х	X.X	Х	x.x	X	X.X	Х	X.X	X	x.x	X	X.X	X	X.X
	ETVAX Full Dose + 10 μg dmLT	X	Х	x.x	х	x.x	Х	x.x	Х	x.x	X	x.x	X	x.x	Х	x.x	X	x.x	X	x.x	Х	X.X
Max Severity Post Baseline	Placebo	X	Х	x.x	х	x.x	Х	x.x	Х	x.x	X	x.x	X	x.x	Х	x.x	X	x.x	X	x.x	Х	X.X
	ETVAX Full Dose	X	Х	x.x	Х	X.X	Х	x.x	Х	x.x	х	x.x	X	x.x	х	x.x	Х	x.x	X	x.x	X	X.X
	ETVAX Full Dose + 10 μg dmLT	X	X	X.X	Х	X.X	Х	X.X	Х	X.X	Х	x.x	Х	x.x	Х	X.X	X	x.x	X	x.x	х	X.X

Note: The "Max Post Baseline" row indicate the maximum severity experienced by each participant at any time point post baseline, including unscheduled assessments. N = Number of participants in the Safety population.

Table 14.3.4.1a: continued Laboratory Results by Parameter, Maximum Severity, Study Day and Treatment Group - Adults

				Hemog	lobin (g/	dL)								
Time Point	Treatment Group	N	No	one	Gra	ild/ ide 1 ow)	Gra	erate/ ide 2 ow)	Gra	ere/ de 3 ow)		Threatening/ Grade 4 (Low)	Mis	ssing
			n	%	n	%	n	%	n	%	n	%	n	%
Baseline	Placebo	X	X	X.X	X	X.X	X	X.X	X	X.X	X	X.X	X	x.x
	ETVAX Full Dose	X	Х	X.X	X	x.x	X	x.x	X	X.X	Х	X.X	X	x.x
	ETVAX Full Dose + 10 μg dmLT	Х	х	X.X	X	X.X	X	X.X	X	x.x	x	X.X	X	x.x
Day 7	Placebo	X	Х	X.X	X	X.X	X	X.X	X	X.X	Х	X.X	X	x.x
	ETVAX Full Dose	X	Х	X.X	X	X.X	X	X.X	X	X.X	Х	X.X	X	x.x
	ETVAX Full Dose + 10 μg dmLT	Х	х	X.X	х	X.X	х	x.x	Х	x.x	х	X.X	х	x.x
Max Severity Post Baseline	Placebo	Х	х	X.X	х	X.X	х	X.X	Х	x.x	x	X.X	х	x.x
	ETVAX Full Dose	X	Х	X.X	X	X.X	X	X.X	X	X.X	Х	X.X	X	x.x
	ETVAX Full Dose + 10 μg dmLT	Х	х	X.X	X	X.X	X	X.X	Х	x.x	х	X.X	X	x.x

Table 14.3.4.1a: continued Laboratory Results by Parameter, Maximum Severity, Study Day and Treatment Group - Adults

			I	Platelet (Counts (1	10 ⁹ /L)								
Time Point	Treatment Group	N	No	one		ild/ de 1 ow)	Gra	erate/ de 2 ow)	Gra	ere/ de 3 ow)	(Threatening/ Grade 4 (Low)	Mis	ssing
			n	%	n	%	n	%	n	%	n	%	n	%
Baseline	Placebo	X	X	X.X	X	X.X	X	X.X	X	X.X	X	X.X	X	X.X
	ETVAX Full Dose	X	X	X.X	X	X.X	X	X.X	X	X.X	X	X.X	X	X.X
	ETVAX Full Dose + 10 μg dmLT	х	X	X.X	X	x.x	Х	x.x	X	X.X	X	X.X	Х	x.x
Day 7	Placebo	X	X	X.X	X	X.X	X	X.X	X	X.X	X	X.X	X	X.X
	ETVAX Full Dose	X	X	X.X	X	X.X	X	X.X	X	X.X	X	X.X	X	X.X
	ETVAX Full Dose + 10 μg dmLT	х	X	X.X	X	x.x	X	x.x	Х	x.x	X	X.X	X	x.x
Max Severity Post Baseline	Placebo	X	X	X.X	X	X.X	X	X.X	X	X.X	X	X.X	X	X.X
	ETVAX Full Dose	Х	X	X.X	X	X.X	X	X.X	X	X.X	X	X.X	X	X.X
	ETVAX Full Dose + 10 μg dmLT	х	X	X.X	X	x.x	Х	x.x	X	X.X	X	X.X	Х	x.x

Table 14.3.4.1a: continued Laboratory Results by Parameter, Maximum Severity, Study Day and Treatment Group - Adults

								White	Bloo	d Cells	10 ⁹ /L											
						Mild/	Grade	1	Mo	oderate	/ Grad	le 2	\$	Severe/0	Grade	3	L		reater	ning/		
			N	one	(L	ow)	(H	igh)	(I	low)	(Hi	igh)	(I	Low)	(H	igh)	(L	(Low) (High)		igh)	Mis	ssing
Time Point	Treatment Group	N	n	%	n	%	n	%	n	%	n	%	n	%	n	%	n	%	n	%	n	%
Baseline	Placebo	X	Х	x.x	X	X.X	х	x.x	х	x.x	х	x.x	х	x.x	X	X.X	X	x.x	X	X.X	X	X.X
	ETVAX Full Dose	X	Х	X.X	X	X.X	х	x.x	х	x.x	х	x.x	х	X.X	х	X.X	Х	x.x	X	X.X	X	X.X
	ETVAX Full Dose + 10 μg dmLT	X	х	x.x	Х	x.x	Х	x.x	X	x.x	Х	x.x	Х	x.x	Х	x.x	Х	X.X	X	x.x	X	X.X
Day 7	Placebo	X	Х	X.X	Х	X.X	х	X.X	Х	X.X	х	x.x	х	X.X	х	X.X	Х	x.x	X	X.X	X	X.X
	ETVAX Full Dose	X	Х	X.X	Х	X.X	х	X.X	Х	X.X	х	x.x	х	X.X	х	X.X	Х	x.x	X	X.X	X	X.X
	ETVAX Full Dose + 10 μg dmLT	X	х	x.x	х	x.x	Х	x.x	Х	x.x	х	X.X	Х	x.x	х	x.x	Х	X.X	X	x.x	Х	X.X
Max Severity Post Baseline	Placebo	X	х	x.x	х	x.x	Х	X.X	Х	x.x	Х	x.x	Х	x.x	Х	X.X	х	x.x	X	x.x	Х	X.X
	ETVAX Full Dose	X	Х	X.X	Х	X.X	х	X.X	Х	X.X	х	x.x	х	X.X	х	X.X	Х	x.x	X	X.X	X	X.X
	ETVAX Full Dose + 10 μg dmLT	X	Х	X.X	X	X.X	Х	X.X	Х	x.x	Х	X.X	Х	x.x	Х	X.X	X	X.X	X	x.x	X	X.X

Note: The "Max Post Baseline" row indicate the maximum severity experienced by each participant at any time point post baseline, including unscheduled assessments.

N = Number of participants in the Safety population.

Table 14.3.4.1a: continued Laboratory Results by Parameter, Maximum Severity, Study Day and Treatment Group - Adults

		Ala	nine An	ninotran	sferase (.	ALT) (U	/L)							
Time Point	Treatment Group	N	No	one	Gra	ild/ de 1 igh)	Gra	erate/ de 2 igh)	Gra	ere/ ide 3 igh)	Gra	ere/ de 4 gh)	Mis	ssing
			n	%	n	%	n	%	n	%	n	%	n	%
Baseline	Placebo	X	X	X.X	X	X.X	X	X.X	X	X.X	X	X.X	X	x.x
	ETVAX Full Dose	Х	X	X.X	Х	X.X	X	X.X	X	X.X	Х	X.X	X	X.X
	ETVAX Full Dose + 10 μg dmLT	х	X	X.X	х	X.X	x	X.X	X	X.X	x	X.X	X	X.X
Day 7	Placebo	X	Х	X.X	Х	X.X	X	X.X	X	X.X	X	X.X	X	X.X
	ETVAX Full Dose	Х	X	X.X	Х	X.X	X	X.X	X	X.X	Х	X.X	X	X.X
	ETVAX Full Dose + 10 μg dmLT	х	х	x.x	х	X.X	х	x.x	х	X.X	х	X.X	х	X.X
Max Severity Post Baseline	Placebo	Х	X	X.X	Х	X.X	X	X.X	X	X.X	Х	X.X	X	X.X
	ETVAX Full Dose	х	Х	X.X	Х	X.X	Х	X.X	X	X.X	Х	X.X	Х	X.X
	ETVAX Full Dose + 10 μg dmLT	х	х	x.x	х	X.X	х	x.x	X	x.x	х	x.x	х	X.X

Table 14.3.4.1a: continued Laboratory Results by Parameter, Maximum Severity, Study Day and Treatment Group - Adults

			C	reatinie	(μmol/I	a)								
Time Point	Treatment Group	N	No	one	Gra	ild/ de 1 gh)	Gra	erate/ de 2 igh)	Gra	ere/ de 3 igh)	Gra	ere/ de 4 gh)	Mis	ssing
			n	%	n	%	n	%	n	%	n	%	n	%
Baseline	Placebo	X	X	X.X	X	X.X	X	X.X	X	X.X	x	X.X	X	X.X
	ETVAX Full Dose	X	X	x.x	X	X.X	X	X.X	X	X.X	X	X.X	X	x.x
	ETVAX Full Dose + 10 μg dmLT	Х	X	X.X	X	x.x	X	x.x	X	X.X	X	x.x	X	x.x
Day 7	Placebo	X	X	x.x	X	X.X	X	X.X	X	X.X	X	X.X	X	X.X
	ETVAX Full Dose	X	X	X.X	X	X.X	Х	X.X	Х	X.X	X	X.X	X	x.x
	ETVAX Full Dose + 10 μg dmLT	Х	X	X.X	х	X.X	х	x.x	х	x.x	X	X.X	X	x.x
Max Severity Post Baseline	Placebo	X	X	x.x	X	X.X	X	X.X	X	X.X	X	X.X	X	x.x
	ETVAX Full Dose	X	X	X.X	X	X.X	X	X.X	X	X.X	X	X.X	X	X.X
	ETVAX Full Dose + 10 μg dmLT	X	X	x.x	X	X.X	X	X.X	X	X.X	X	X.X	X	x.x

TABLE 14.3.4.1b:

Laboratory Results by Parameter, Maximum Severity, Study Day, and Treatment Group - Toddlers (24 - 59 Months)

Programming Note: Use the same Table shell as Table 14.3.4.1(a). Treatments to summarize are the following: Placebo, ETVAX 1/4 Dose, ETVAX (highest safe dose) + 2.5 μ g dmLT, ETVAX (highest safe dose) + 5 μ g dmLT, ETVAX (highest safe dose) + 10 μ g dmLT

TABLE 14.3.4.1c:

Laboratory Results by Parameter, Maximum Severity, Study Day, and Treatment Group - Young Children (12 - 23 Months)

Programming Note: Use the same Table shell as Table 14.3.4.1(a). Treatments to summarize are the following: Placebo, ETVAX 1/4 Dose, ETVAX (highest safe dose) + 2.5 µg dmLT, ETVAX (highest safe dose) + 5 µg dmLT

TABLE 14.3.4.1d:

Laboratory Results by Parameter, Maximum Severity, Study Day, and Treatment Group - Infants (6 - 11 Months)

Programming Note: Use the same Table shell as Table 14.3.4.1(a). Treatments to summarize are the following: Placebo, ETVAX 1/8 Dose, ETVAX 1/4 Dose, ETVAX (highest safe dose) + 2.5 µg dmLT, ETVAX (highest safe dose) + 5 µg dmLT

TABLE 14.3.4.2a: Summary Statistics of Laboratory Results by Parameter, Study Visit and Treatment Group - Adults

Laboratory Parameter	Time Point	Treatment Group	N	Mean	Standard Deviation	Median	25th - 75th Percentile	Min, Max
Hemoglobin (g/dL)	Baseline	Placebo	X	XX.X	XX.X	xx.x	xx.x - xx.x	xx.x, xx.x
		ETVAX Full Dose	X	XX.X	XX.X	xx.x	xx.x - xx.x	xx.x, xx.x
		ETVAX Full Dose + 10 μg dmLT	X	XX.X	XX.X	xx.x	xx.x - xx.x	xx.x, xx.x
	Day 7	Placebo	X	XX.X	XX.X	xx.x	xx.x - xx.x	xx.x, xx.x
		ETVAX Full Dose	X	XX.X	XX.X	xx.x	xx.x - xx.x	XX.X, XX.X
		ETVAX Full Dose + 10 μg dmLT	X	XX.X	XX.X	xx.x	xx.x - xx.x	xx.x, xx.x
	Day 7, Change from Baseline	Placebo	X	XX.X	XX.X	xx.x	xx.x - xx.x	xx.x, xx.x
		ETVAX Full Dose	X	XX.X	XX.X	xx.x	xx.x - xx.x	xx.x, xx.x
		ETVAX Full Dose + 10 μg dmLT	Х	xx.x	XX.X	XX.X	XX.X - XX.X	xx.x, xx.x
Platelet Count (10 ⁹ /L)	Baseline	Placebo	X	xx.x	XX.X	XX.X	xx.x - xx.x	xx.x, xx.x
		ETVAX Full Dose	Х	XX.X	XX.X	xx.x	xx.x - xx.x	xx.x, xx.x
		ETVAX Full Dose + 10 μg dmLT	Х	XX.X	XX.X	xx.x	xx.x - xx.x	xx.x, xx.x
	Day 7	Placebo	Х	xx.x	XX.X	xx.x	xx.x - xx.x	xx.x, xx.x
		ETVAX Full Dose	Х	xx.x	XX.X	xx.x	xx.x - xx.x	xx.x, xx.x
		ETVAX Full Dose + 10 μg dmLT	X	XX.X	XX.X	xx.x	xx.x - xx.x	XX.X, XX.X
	Day 7, Change from Baseline	Placebo	X	XX.X	XX.X	xx.x	xx.x - xx.x	xx.x, xx.x
		ETVAX Full Dose	X	XX.X	XX.X	xx.x	xx.x - xx.x	XX.X, XX.X
		ETVAX Full Dose + 10 μg dmLT	X	XX.X	XX.X	xx.x	xx.x - xx.x	xx.x, xx.x

Note: Continue for all laboratory tests: White Blood Cells (10⁹/L), ALT (U/L), Creatinine (µmol/L).

TABLE 14.3.4.4a: Listing of Abnormal Laboratory Results - Adults

Participant ID	Arm	Sex	Age (years)	Planned Time Point	Actual Study Day	Laboratory Parameter (Units)	Result (Severity)	Relationship to Treatment	If Not Related, Alternate Etiology	Action Taken with Study Treatment	Participant Discontinued Due to Result?

[Implementation Note: This listing only includes abnormal laboratory results. A complete listing of all laboratory results is included in the listings document. In the Laboratory Parameter column, indicate the units after the parameter, e.g., Hemoglobin (g/dL). The grade will be included in parentheses after the result, e.g., 16.2 (Grade 1).]

TABLE 14.3.4.4b: Listing of Abnormal Laboratory Results - Toddlers (24 - 59 Months)

Participant ID	Arm	Sex	Age (months)	Planned Time Point	Actual Study Day	Laboratory Parameter (Units)	Result (Severity)	Relationship to Treatment	If Not Related, Alternate Etiology	Action Taken with Study Treatment	Participant Discontinued Due to Result?

[Implementation Note: This listing only includes abnormal laboratory results. A complete listing of all laboratory results is included in the listings document. In the Laboratory Parameter column, indicate the units after the parameter, e.g., Hemoglobin (g/dL). The grade will be included in parentheses after the result, e.g., 16.2 (Grade 1).]

[figure not shown]
TABLE 14.3.4.4c: Listing of Abnormal Laboratory Results - Young Children (12 - 23 Months)

Programming Note: Use the same Table shell as Table 14.3.4.4(b).

TABLE 14.3.4.4d: Listing of Abnormal Laboratory Results - Infants (6 - 11 Months)

Programming Note: Use the same Table shell as Table 14.3.4.4(b).

FIGURE 14.3.5.1a:
Vital Sign Measurements by Scheduled Visits: Mean Changes from Baseline by Vital Sign and Treatment Group - Adults

Note: Continue for all vital signs: Heart Rate (beats/min)

FIGURE 14.3.5.1b:

Vital Sign Measurements by Scheduled Visits: Mean Changes from Baseline by Vital Sign and Treatment Group - Toddlers (24 - 59 Months)

Programming Note: Use same format as Figure 14.3.5.1a - except use treatment groups: ETVAX 3.5 mL, ETVAX 7mL, ETVAX 14 mL, ETVAX ## + 2.5 µg dmLT, ETVAX ## + 5 µg dmLT, ETVAX ## + 10 µg dmLT, Placebo

FIGURE 14.3.5.1c:

Vital Sign Measurements by Scheduled Visits: Mean Changes from Baseline by Vital Sign and Treatment Group - Young Children (12 - 23 Months)

Programming Note: Use same format as Figure 14.3.5.1a - except use treatment groups: ETVAX 3.5 mL, ETVAX 7mL, ETVAX ## + 2.5 µg dmLT, ETVAX ## + 5 µg dmLT, Placebo

FIGURE 14.3.5.1d:

Vital Sign Measurements by Scheduled Visits: Mean Changes from Baseline by Vital Sign and Treatment Group - Infants (6 - 11 Months)

Programming Note: Use same format as Figure 14.3.5.1a - except use treatment groups: ETVAX 1.75 mL, ETVAX 3.5 mL, ETVAX 7mL, ETVAX ## + 2.5 µg dmLT, ETVAX ## + 5 µg dmLT, Placebo

TABLE 14.3.6a: Number and Percentage of Participants with Prior and Concurrent Medications by Treatment Group - Adults

	Plac (N=		ETVAX Full Dose (N=X)		ETVAX Full Dose + 10 μg dmLT (N=X)		All Participants (N=X)	
Medication Name	n	%	n	%	n	%	n	%
Any Medication	X	x.x	X	X.X	Х	X.X	Х	x.x
[Medication 1]	X	x.x	X	X.X	Х	x.x	X	x.x
[Medication 2]	X	x.x	X	X.X	Х	X.X	Х	x.x
[Medication 3]	X	x.x	X	X.X	X	x.x	X	X.X

N = Number of participants in the Safety population. n = Number of participants reporting taking at least one medication in the medication class. A participant will only be counted once in each row.

TABLE 14.3.6b:

Number and Percentage of Participants with Prior and Concurrent Medications by Treatment Group - Toddlers (24 - 59 Months)

	Placebo (N=XX)			ETVAX 1/4 Dose (N=XX)		ETVAX 1/2 Dose (N=XX)		ETVAX Full Dose (N=XX)		Combined ETVAX Alone (N=XX)	
Medication Name	n	%	n	%	n	%	n	%	n	%	
Any Medication	X	X.X	X	X.X	X	X.X	X	X.X	X	X.X	
[Medication 1]	Х	X.X	X	X.X	X	X.X	X	X.X	Х	X.X	
[Medication 2]	Х	X.X	X	X.X	X	X.X	X	X.X	Х	X.X	
[Medication 3]	X	x.x	x	x.x	X	X.X	X	x.x	X	X.X	

N = Number of participants in the Safety population. n = Number of participants reporting taking at least one medication in the medication class. A participant will only be counted once in each row.

	ETV (highest sa +2.5 μg (N=)	afe dose) dmLT	(highest s +5 μg	ETVAX (highest safe dose) +5 µg dmLT (N=XX)		ETVAX (highest safe dose) +10 µg dmLT (N=XX)		Combined ETVAX + dmLT (N=XX)		All Participants (N=XX)	
Medication Name	n	%	n	%	n	%	n	%	n	%	
Any Medication	Х	X.X	X	X.X	X	X.X	X	X.X	X	X.X	
[Medication 1]	Х	X.X	X	X.X	X	X.X	X	X.X	X	X.X	
[Medication 2]	Х	X.X	X	X.X	X	X.X	X	X.X	X	X.X	
[Medication 3]	X	X.X	X	X.X	X	X.X	X	X.X	X	X.X	

N = Number of participants in the Safety population. n = Number of participants reporting taking at least one medication in the medication class. A participant will only be counted once in each row.

TABLE 14.3.6c:
Number and Percentage of Participants with Prior and Concurrent Medications
by Treatment Group - Young Children (12 - 23 Months)

	Placebo (N=XX)		ETVAX 1/4 Dose (N=XX)		ETVAX		Combined ETVAX Alone (N=XX)	
Medication Name	n	%	n	%	n	%	n	%
Any Medication	X	X.X	X	X.X	X	X.X	X	X.X
[Medication 1]	X	X.X	х	X.X	X	X.X	X	X.X
[Medication 2]	X	X.X	х	x.x	X	X.X	X	X.X
[Medication 3]	X	X.X	х	x.x	X	X.X	X	X.X

N = Number of participants in the Safety population. n = Number of participants reporting taking at least one medication in the medication class. A participant will only be counted once in each row.

	ETVAX (highest safe dose) (l +2.5 µg dmLT (N=XX)		(highest s +5 μg	ETVAX (highest safe dose) +5 µg dmLT (N=XX)		ETVAX LLT XX)	All Participants (N=XX)		
Medication Name	n	%	n	%	n	%	n	%	
Any Medication	X	X.X	X	X.X	X	X.X	X	X.X	
[Medication 1]	X	X.X	X	X.X	X	X.X	X	X.X	
[Medication 2]	X	X.X	X	X.X	X	X.X	X	X.X	
[Medication 3]	Х	X.X	X	x.x	X	x.x	X	X.X	

N = Number of participants in the Safety population. n = Number of participants reporting taking at least one medication in the medication class. A participant will only be counted once in each row.

TABLE 14.3.6d:
Number and Percentage of Participants with Prior and Concurrent Medications
by Treatment Group - Infants (6 - 11 Months)

		cebo XX)	ETVAX 1/8 Dose (N=XX)		ETVAX 1/4 Dose (N=XX)		ETVAX 1/2 Dose (N=XX)		Combined ETVAX Alone (N=XX)	
Medication Name	n	%	n	%	n	%	n	%	n	%
Any Medication	X	X.X	X	x.x	X	x.x	х	x.x	X	X.X
[Medication 1]	X	X.X	X	x.x	X	x.x	х	x.x	X	X.X
[Medication 2]	X	X.X	X	x.x	X	x.x	х	x.x	X	X.X
[Medication 3]	X	X.X	X	X.X	х	X.X	X	X.X	Х	X.X

N = Number of participants in the Safety population. n = Number of participants reporting taking at least one medication in the medication class. A participant will only be counted once in each row.

	ETVAX (highest safe dose) + 2.5 µg dmLT (N=XX)		ETV (highes dos + 5 µg (st safe se) dmLT	+ dr	AX	All Participants (N=XX)		
Medication Name	n %		n	%	n	%	n	%	
Any Medication	X	x.x	X	X.X	X	X.X	х	X.X	
[Medication 1]	X	x.x	X	X.X	X	X.X	X	X.X	
[Medication 2]	X	x.x	X	x.x	X	X.X	х	X.X	
[Medication 3]	X	X.X	X	X.X	Х	X.X	Х	X.X	

N = Number of participants in the Safety population. n = Number of participants reporting taking at least one medication in the medication class. A participant will only be counted once in each row.

PATH Protocol: VAC 014/OEV-122 ERC/PR-14127
Statistical Analysis Plan: Appendix II - Listings

